PAR-Q	Physical Activity Readiness Questionnaire
PI	Principal Investigator
PREHAB	Prehabilitation
PROMIS-29	Patient-Reported Outcomes Measurement Information System
PROMIS Cancer Function	Patient-Reported Outcomes Measurement Information System Cancer Function
QMC	Quality Management Core
SOC	Standard of Care
SOCCI	Samuel Oschin Comprehensive Cancer Institute
UPIRSO	Unanticipated Problems Involving Risk to Subjects or Others

STUDY SCHEMA

Primary endpoint: Feasibility of a PREHAB program evaluated by attendance. The program will be considered feasible if at least 50% of participants attend at least 60% of exercise sessions.

PREHAB- Prehabilitation

STUDY SUMMARY

Title	A Supervised Prehabilitation Exercise Program for Patients with Pancreatic Cancer
Short Title	Exercise program for pancreatic cancer
Protocol Number	IIT2021-18-[name]-PREHAB
Phase	Pilot
Methodology	Single Arm
Study Duration	12 Months
Study Center(s)	Single Center
Objectives	The primary objective is to test the feasibility of a supervised prehabilitation program for patients with pancreatic cancer.
Number of Subjects	16 subjects
Diagnosis and Main Inclusion Criteria	
Main Inclusion Criteria:
 
 -Pancreatic cancer diagnosis (any stage) -Age ≥ 18 years -Independent ambulation and activities of daily living -Godin-Shephard Leisure-Time Physical Activity Questionnaire score of ≤ 23 -Physically able to participate in study assessments -Answers no to all questions on PAR-Q OR is cleared to participate by the study physician -Written informed consent obtained from subject and ability for subjects to comply with the requirements of the study
Study Product(s), Dose, Route, Regimen	Supervised exercise PREHAB program
Duration of administration	6 weeks
Reference therapy	None
Statistical Methodology	The primary analysis will test the hypothesis of feasibility using an one-sided exact Binomial test at 25% significance level. If 10 or more patients attend a minimum of 60% of exercise sessions during the initial 6-week period, then the study will be declared feasible.

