2.3.8 To assess the impact of a PREHAB program on weight and BMI

2.4 Endpoints**2.4.1 Primary Efficacy Endpoint**

Feasibility – REHAB session feasibility is defined as at least 10 of the 16 participants attending at least 60% of scheduled sessions

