8.0 STATISTICAL CONSIDERATIONS

8.1 Sample Size and Randomization

We plan to enroll 16 patients to reach 80% power testing the hypothesis that the proportion of patients with attendance at least 60% of exercise sessions during the initial 6-week period is greater than 50% using an one-sided exact Binomial test at 25% significance level. The actual significance level is 22.7%.

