8.3 Data Analyses/Study Endpoints

Primary Objective: The primary analysis will test the hypothesis of feasibility using an one-sided exact Binomial test at 25% significance level. If 10 or more patients attend a minimum of 60% of exercise sessions during the initial 6-week period, then the study will be declared feasible.

Secondary Endpoints: We will present descriptive measures for secondary endpoints with spaghetti and profile plots for repeated measures

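### The Study Schema sets the feasibility pass mark at 50% of participants (8 of 16), but the Study Summary and Sections 2.4.1 and 8.3 set it at 10 of 16

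*Combined protocol and SAP*

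**What the plan says.** The plan states the pass mark for the primary endpoint in four places.

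- **Study Schema:** "The program will be considered feasible if at least 50% of participants attend at least 60% of exercise sessions". No count is given, and no null proportion or error rate is attached.
- **Study Summary, Statistical Methodology row:** 10 or more patients meeting the 60% attendance criterion. The wording is the same as in Section 8.3.
- **Section 2.4.1:** feasibility is "defined as at least 10 of the 16 participants attending at least 60% of scheduled sessions".
- **Section 8.3:** "If 10 or more patients attend a minimum of 60% of exercise sessions during the initial 6-week period, then the study will be declared feasible".

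Section 8.1 gives the design behind the rule: "We plan to enroll 16 patients to reach 80% power testing the hypothesis". The claim under test is that more than half of patients meet the attendance criterion, so the null proportion is 50%. The test is a one-sided exact binomial with a nominal level of 25%, and the section reports an actual level of 22.7%. It does not give the alternative proportion at which the 80% power is reached.

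**The concern.** The schema and the other three statements describe the same endpoint, the same attendance criterion and the same 16 participants, yet they give different pass marks. The schema's figure of 50% is the value that Section 8.1 tests against, so the null proportion appears to have been written in as the success threshold.

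Feasibility is the sole primary objective and the only endpoint with a formal test. With 8 or 9 attenders, the protocol contains one sentence that supports a feasible result and three that deny it. The test already allows a one-sided level of 25%. A second, looser threshold left in the document makes it easier to choose between them after the data are seen, or to report against the wrong one.

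**Working it through.** **Inputs.** N = 16 (Section 8.1, Study Summary). Null proportion 0.50, one-sided exact binomial test, nominal level 0.25, actual level 22.7% (Section 8.1). Cut-off 10 (Study Summary, Sections 2.4.1 and 8.3). Cut-off in the schema: 0.50 × 16 = 8. As a proportion, 10/16 = 62.5%.

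**Formula.** With X the number of participants who meet the attendance criterion and p the true proportion,

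P(X ≥ r | p) = Σ from k = r to 16 of C(16, k) p^k (1 − p)^(16 − k).

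**Step 1: reproduce the stated level.** At p = 0.50 each term is C(16, k)/65,536.

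P(X ≥ 10) = (8008 + 4368 + 1820 + 560 + 120 + 16 + 1)/65,536 = 14,893/65,536 = 0.2272.

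This is the 22.7% in Section 8.1, so that figure is correct for a cut-off of 10.

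**Step 2: try the neighbouring cut-offs at p = 0.50.**

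| Cut-off | P(X ≥ cut-off) | Within the nominal 25%? |
|---|---|---|
| 8 (schema) | 0.5982 | No |
| 9 | 0.4018 | No |
| 10 (Summary, 2.4.1, 8.3) | 0.2272 | Yes |
| 11 | 0.1051 | Yes |

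Ten is the smallest cut-off that respects the 25% limit, and the only one that gives 22.7%.

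**Step 3: how often would the two rules disagree?** They disagree when X = 8 or 9, so the probability is P(X ≥ 8) − P(X ≥ 10).

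| True proportion | P(X ≥ 8) | P(X ≥ 10) | Rules disagree |
|---|---|---|---|
| 0.40 | 0.284 | 0.058 | 0.23 |
| 0.50 | 0.598 | 0.227 | 0.37 |
| 0.60 | 0.858 | 0.527 | 0.33 |
| 0.65 | 0.933 | 0.688 | 0.24 |
| 0.70 | 0.974 | 0.825 | 0.15 |

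**Step 4: the 80% power.** The documents give no alternative, so this figure cannot be reproduced from their inputs. Solving backwards for the 10-of-16 rule, power is exactly 80% at p ≈ 0.69 (0.8003 at 0.69) and 82.5% at p = 0.70. Either could have been the planning value.

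**The case against.** **The operative rule is not really in doubt.** This is the strongest objection, and it largely stands. Three statements say 10, the Study Summary follows the schema directly, and the stated 22.7% fits no other cut-off. A statistician working from Sections 2.4.1 and 8 would apply 10 of 16. That makes the correction easy, but the schema still carries a complete and contrary rule for the primary endpoint.

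**The schema might be stating the hypothesis rather than the decision rule.** This does not remove the conflict. The sentence is a condition on what participants do, followed by a conclusion about the program. It also does not match the hypothesis: Section 8.1 tests for a proportion above 50%, whereas the schema accepts 50% itself.

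**It is a pilot with a 25% level.** This is true, and the result should not be called confirmatory. It is still the one formal decision that the study makes.

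A reader might also infer three stronger things that the documents do not support:

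- *That the trial has a 60% false-positive rate, or that the stated 22.7% is wrong.* The 22.7% reproduces. The schema states no null and no error rate, so 59.8% arises only if its cut-off is used for the Section 8.1 test.
- *That 80% power holds only for the 10-of-16 rule.* Any cut-off reaches 80% at some proportion; the 8-of-16 rule does so at p = 0.573.
- *That the design alternative was 0.69.* That value is solved backwards, and 0.70 fits the wording equally well.

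**Conclusion.** The schema threshold is wrong as written. It is an internal inconsistency; no calculation in the plan is shown to be in error. The schema passes the program at 8 of 16, and the Study Summary, Section 2.4.1 and Section 8.3 pass it at 10 of 16. The conclusions are opposite for 8 or 9 attenders.

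The conflict itself rests on nothing beyond the stated 16 participants. The probabilities of landing in it (0.37 at a true proportion of 0.50, 0.33 at 0.60) assume 16 evaluable patients who attend or not independently of each other. The 59.8% further assumes a true proportion of exactly 0.50 and the schema cut-off applied to the Section 8.1 test.

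The unstated alternative in Section 8.1 is a minor omission. It leaves the 80% unverifiable, but it does not show it to be wrong.

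**What to change.** Reword the schema sentence so that the program counts as feasible when 10 or more of the 16 participants (62.5%) reach 60% attendance, and name 50% there as the null proportion of the test. This makes all four statements agree with each other and with the 22.7%.

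As a minor addition, the sponsor should state in Section 8.1 the alternative proportion actually used for the 80% power. The review should not supply it.

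The cost is one corrected sentence and one added figure. Sample size, procedures and patient care do not change. The correction should be in place before the attendance data are analysed, so that the threshold is clearly not chosen in the light of the result.

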1.0 BACKGROUND AND RATIONALE

1.1 Disease Background

During 2022, there is estimated to be 62,000 new cases of pancreatic cancer, causing an estimated 49,000 deaths¹. Individuals who develop pancreatic cancer tend to be older, with 70% of pancreatic diagnoses occurring in those ≥ 65 years². As individuals age their risk of comorbidities such as sarcopenia and frailty increase³. Sarcopenia is the progressive loss of skeletal muscle mass, tone, quality and strength and has been reported to affect 65% of pancreatic cancer patients⁴. Results from a recent meta-analysis suggest sarcopenia is associated with decreased long-term survival and is an important prognostic factor in recurrent pancreatic cancer^{4,5}.

1.2 Study Background

1.2.1 Prehabilitation (PREHAB)

PREHAB is the process of improving the functional capability and psychological health of the individual to reduce the incidence and/or severity of future impairments⁶. While PREHAB has most commonly been described as occurring prior to neoadjuvant therapy and surgery it can also occur in nonsurgical patients and concurrently with neoadjuvant treatment^{6,7}. The foundation of PREHAB is functional exercise yet can be multimodal in nature and can include additional components such as nutritional support, smoking cessation, and stress reduction⁹. PREHAB sessions are typically delivered through structured programs and have been shown to have a number of benefits such as improvements in functional activity and decreased postoperative complications⁸.

1.2.2 Clinical Data

Multiple studies have reported the positive effects of PREHAB in cancer patients⁹. A recent systematic review reported improved functional activity and survival outcomes in a range of cancer types following moderate to vigorous intensity exercise participation¹⁸. In colorectal cancer patients, PREHAB programs have shown to improve VO₂ max and functional activity (6 minute walk tests)^{10,11}. In patients undergoing cystectomy, PREHAB has been shown to increase power output and performance with activities of daily living¹². A recent review by Garcia et al, reported improved pulmonary function, less days spent in the hospital and reduced risk of postoperative complications in lung cancer patients following participation in a PREHAB program¹³. An additional Cochrane review of 167 patients with non-small cell lung cancer reported preoperative exercise training may reduce postoperative pulmonary complications, decrease postoperative hospital lengths of stay, and improved exercise capacity¹⁴. In a study by Ngo-Huang et al, 50 pancreatic cancer participants participated in a home-based multimodal program including at least 60 minutes moderate intensity aerobic exercise weekly and at least 60 minutes full body strengthening exercises weekly. The mean duration of the exercise program was 16 weeks and patients were found to have improved physical function and health related quality of life¹⁵.

There is currently inconsistency surrounding PREHAB delivery method and use of additional nutritional dietary supplementation. In a recent systematic review of pancreatic cancer PREHAB studies (n=6) there was considerable variation seen in; when to initiate PREHAB, exercise programming duration, supervision of sessions, exercise types, dietary supplementation, and reporting of outcomes⁸. Favorable outcomes were reported in studies which started PREHAB prior to surgery, were ≥ 6 -week in duration, included supervised sessions and included moderate intensity aerobic training combined with resistance training.

1.3 Rationale

PREHAB has previously been reported to significantly improve quality of life, physical function and decreased post-operative complications in several cancer populations. Given the positive benefits reported in both physical function and quality of life post participating in PREHAB sessions the purpose of this study is to demonstrate the feasibility of a multimodal supervised PREHAB program in pancreatic cancer patients. Secondary aims include assessing safety and exploring benefits in sarcopenia, quality of life and functional performance.

2.0 STUDY OBJECTIVES**2.1 Primary Objective**

2.1.1 To assess the feasibility of a 6-week supervised PREHAB program for pancreatic cancer patients

2.2 Secondary Objective

2.2.1 To evaluate the safety of a 6-week supervised PREHAB program for pancreatic cancer patients

2.3 Exploratory Objectives

2.3.1 To assess the impact of a PREHAB program on sarcopenia

2.3.2 To assess the impact of a PREHAB program on health-related quality of life including domains of physical function, fatigue, and social participation

2.3.3 To assess the impact of a PREHAB program on functional performance including strength and endurance

2.3.4 To assess the association between a PREHAB program and healthcare utilization including number of hospitalizations and length of stay

2.3.5 To assess the impact of a PREHAB program on post-operative outcomes including length of stay and complication rates

2.3.6 To assess the impact of a PREHAB program on continuous activity and sleep patterns

2.3.7 To assess the impact of a validated, web-based, health self-management guide designed for individuals with chronic illnesses (www.painguide.com)

2.3.8 To assess the impact of a PREHAB program on weight and BMI

2.4 Endpoints**2.4.1 Primary Efficacy Endpoint**

Feasibility – REHAB session feasibility is defined as at least 10 of the 16 participants attending at least 60% of scheduled sessions

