5.1 PREHAB Components

5.1.1 Functional Exercise

Participants will attend 3 x weekly 1hr in-person supervised exercise sessions with a trained exercise physiologist or personal trainer for a 6-week period. Sessions will be scheduled around the participants and the trainer's availability. Sessions will be held in the hospital gym at Cedars-Sinai – [name]. During these sessions patients will undergo aerobic and resistance training.

Missed Sessions: Patients will be strongly advised not to miss any sessions. Sessions missed due to cancellations from the study team or participant (due to sickness, holidays, etc.) will be made during an optional 7th week following the 6-week intervention. There will be up to three make-up sessions. Patients will not be required to attend these make-up sessions but if they do not attend it will count as a missed session.

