5.6 Subject Replacement

Subjects who withdraw from the study prior to their PREHAB session 1 will be replaced.

Subjects who attend at least the first session will be evaluable for both the primary and secondary endpoint analysis. To be evaluable for exploratory endpoints subjects will need to complete the 3 month follow up visit.

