6.2.4 Review of SOC Lab Results

- Participants are anticipated to be undergoing neoadjuvant therapies concurrently with study participation. These therapies may impact the participants circulating cytokines, thus rendering them ineligible to participate in physical activity.

Prior to each PREHAB session exercise physiologist or personal trainer will check the participants' medical records for the most recent SOC lab results. To participate all 3 thresholds must be met:

- absolute neutrophils >0.5 $1000/UL$
- platelets > 50 $1000/UL$
- hemoglobin >8 g/dl

If one or more of these thresholds are not met the PI will be notified and the participant will be unable to participate in the exercise session. Sessions will resume when all lab values have reached the required thresholds or at the PI's discretion.

These thresholds were determined by the cancer rehabilitation physiatrists and referring pancreatic oncologists and are in line with other cancer activity recommendations^{19,20}.

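### The attendance denominator of the primary endpoint is worded inconsistently and never fixed, so one permitted reading of 2.4.1 credits a patient who stops early as an attender

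*Combined protocol and SAP*

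**What the plan says.** The per-patient attendance criterion is worded in three ways:

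- Section 2.4.1 (primary endpoint): "feasibility is defined as at least 10 of the 16 participants attending at least 60% of scheduled sessions".
- Section 8.3 (decision rule): "If 10 or more patients attend a minimum of 60% of exercise sessions during the initial 6-week period". The Study Summary and 8.1 use the same six-week window.
- Study Schema: "The program will be considered feasible if at least 50% of participants attend at least 60% of exercise sessions", with no window.

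Four other sections bear on what the denominator is:

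- Section 5.1.1 sets the program: "Participants will attend 3 x weekly 1hr in-person supervised exercise sessions" for six weeks. It adds: "Sessions will be scheduled around the participants and the trainer's availability". Sessions cancelled by the study team or the participant, sickness included, can be made up in a seventh week, up to three of them: "Patients will not be required to attend these make-up sessions but if they do not attend it will count as a missed session".
- Section 5.6: "Subjects who attend at least the first session will be evaluable for both the primary and secondary endpoint analysis". Only those who withdraw before session 1 are replaced.
- Section 6.2.4 bars a participant from a session when laboratory thresholds are not met: "Sessions will resume when all lab values have reached the required thresholds or at the PI's discretion".
- Section 6.6 lets patients leave the intervention or the study at any time, or be removed.

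The current exclusion criteria (4.2) contain no bar on resection during the program; section 11.1.3 records that one was removed.

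**The concern.** The go/no-go verdict rests on one fraction per patient, and the plan does not fix its denominator. Only the endpoint section says *scheduled*, and that word can vary between patients. A patient who leaves after two weeks stays among the 16, yet nothing says whether the remaining four weeks of sessions were ever scheduled for that patient.

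The case is foreseeable. Section 4.1 admits any stage, 6.2.4 expects concurrent neoadjuvant therapy, and surgery during the program is no longer excluded. Since the booked number cannot reasonably exceed the planned number, counting only booked sessions can raise a patient's percentage but never lower it. Any error from that reading therefore runs towards declaring the program feasible, by crediting patients who did not receive the six-week program named in the primary objective (2.1.1). If the choice is left until attendance is known, the verdict also depends on a decision made after seeing the data.

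**Working it through.** **Inputs.** 16 patients, null rate 50%, one-sided exact binomial test at a nominal 25%, actual level 22.7% (8.1); cut-off 10 (2.4.1, 8.3); three sessions a week for six weeks (5.1.1); 60% attendance threshold. The number of early stoppers is not in the documents and is assumed below.

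**1. The plan's own figure.** With X ~ Bin(16, 0.5), P(X ≥ 10) = (8008 + 4368 + 1820 + 560 + 120 + 16 + 1)/65536 = 14893/65536 = 0.227. This reproduces the stated 22.7%. A cut-off of 9 gives 0.402, so 10 is the smallest cut-off within 25%.

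**2. Threshold on the full program.** 3 × 6 = 18 sessions and 0.60 × 18 = 10.8, so 11 are needed (11/18 = 61.1%; 10/18 = 55.6% falls short).

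**3. Threshold if only sessions booked up to the stop count.**

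| Booked before stopping | Fewest attended to reach 60% | Share of 18 |
|---|---|---|
| 1 | 1 | 6% |
| 3 | 2 | 11% |
| 5 | 3 | 17% |
| 6 | 4 | 22% |
| 9 | 6 | 33% |
| 18 | 11 | 61% |

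**4. Effect on the verdict (illustration).** Suppose k of the 16 stop early after reaching 60% of their booked sessions, and each of the other 16 − k has a 50% chance of being an attender. If the k are credited, the trial succeeds when at least 10 − k of the others attend. If they are scored as non-attenders, at least 10 of the others must attend.

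| k (assumed) | Credited | Scored as non-attenders |
|---|---|---|
| 0 | 22.7% | 22.7% |
| 1 | P(≥ 9 of 15) = 9949/32768 = 30.4% | P(≥ 10 of 15) = 4944/32768 = 15.1% |
| 2 | P(≥ 8 of 14) = 6476/16384 = 39.5% | P(≥ 10 of 14) = 1471/16384 = 9.0% |

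**5. Make-up sessions.** A patient with 8 sessions in weeks 1 to 6 and 3 make-ups in week 7 has 11 of 18 (61.1%) if make-ups count, and 8 of 18 (44.4%) if they do not. Section 5.1.1 implies that they count; the window in 8.1 and 8.3 implies that they do not. A rule of 11 of 18 therefore also has to say which.

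**The case against.** The other side has substantial points.

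- The analysis text gives a six-week window, and three sessions a week over six weeks reads naturally as 18. This stands as the more natural reading of 8.3. A window still does not say whether sessions that fall after a patient has left are counted, and 2.4.1 uses a different word.
- A reader might infer that toxicity in general shrinks the denominator. Section 5.1.1 does not support that: a session cancelled for sickness and not made up counts as missed, so it stays in. That rule covers cancellations, however, and does not mention withdrawal, removal or surgery.
- A reader might infer that a laboratory hold takes sessions out, for example that a two-week hold leaves 12. Section 6.2.4 does not say so. It describes a session in which the participant may not take part, and when sessions restart; it is silent on counting.
- Scheduling around availability concerns the timing of sessions. It does not say that fewer than 18 will be booked.
- Keeping everyone who attends session 1 in the evaluable set (5.6) fits an intention to count early stoppers against feasibility. That is plausible, but it is nowhere stated.
- The contrasts of 30% with 15%, and 40% with 9%, look like a doubling and a fourfold rise. The lower figures set the stoppers to failure and the rest at 50%, so the average rate is 7.5/16 = 46.9% or 7/16 = 43.8%, below the null. The design's 22.7% is the fairer reference.
- Attendance at sessions offered measures adherence; attendance out of 18 measures whether the program can be delivered. How to score lab-hold and study-cancelled sessions is partly a choice between the two. This stands, and the sponsor should make that choice in writing.

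**Conclusion.** The denominator of the primary endpoint is worded inconsistently and not fixed, and the scoring of patients who withdraw, are removed or have surgery after session 1 is undefined. On one permitted reading of 2.4.1, such a patient can count as an attender after a handful of sessions. It would go too far to say that the plan adopts that reading, or that its verdict is biased as written: no section says that the scheduled number falls when a patient stops, and none says that an early stopper is a non-attender.

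In size, one or two credited stoppers move the chance of declaring feasibility from 22.7% to 30% or 40%. This assumes that number of stoppers, that each reached 60% before stopping, and a 50% rate in the others. With a cut-off of 10 of 16, one or two classifications can decide the result. The stated significance level is correct, and the sample size is not in question here.

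**What to change.** In 2.4.1, 8.3 and the Study Summary, and in matching words in 8.1 and the Study Schema:

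1. Define an attender as an evaluable participant who completes at least 11 of the 18 planned supervised sessions.
2. State that planned sessions falling after withdrawal, removal or surgery stay in the denominator as not attended.
3. State, consistently with the missed-session rule in 5.1.1, how lab-hold sessions, study-cancelled sessions and week-7 make-ups count, and align the six-week window in 8.1 and 8.3 with that choice. If any category is to leave the denominator, write down the exception and the threshold that then applies.
4. List reasons for non-attendance descriptively, so that low adherence can be told apart from a program that could not be delivered.

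Section 8.2 should be reconciled at the same time: it limits the analysed data to subjects who reached 60% participation, which conflicts with 5.6.

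The cost is a wording change, made before attendance is analysed, with no new data. The attendance figure may come out slightly less favourable. The sample size of 16, the 22.7% level and the 10-of-16 cut-off do not change.
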